3.1.1 Rationale of Study Design

This study is designed to demonstrate improvement in the percentage of TIR with Soliqua 100/33 in patients with very uncontrolled T2DM (HbA1c \geq 9%-13%) after 3 months of stable treatment with 2+ OADs with or without additional GLP-1 RA therapy.

Continuous glucose monitoring has significantly improved the ability to monitor glycemic variability throughout the day. Data from CGM can be critical in making daily treatment decisions and quantifying TIR, which provides more actionable information than HbA1c alone (Battelino et al 2019). Continuous glucose monitoring is a much-improved measure of TIR compared with SMPG (ie, hundreds of values to analyze versus a single measure in time), to truly understand glycemic variability in people with T2DM.

In a previous post hoc analysis, treatment with Soliqua 100/33 improved measures of glycemic variability (ie, 7-point blood glucose data) in patients uncontrolled on either oral or insulin therapies more than its individual components (ie, lixisenatide or insulin glargine U100). This finding was attributed to the complementary reductions of both fasting and postprandial hyperglycemia (Aronson et al 2019). Clinicians frequently request CGM measures to better understand their patients' TIR, time above range (TAR), and time below range (TBR). Hence, the current study is intended to replicate and enhance the results from the 7-point blood glucose study, but using CGM. Measures such as TIR, coefficient of variation (CV), TAR, TBR, and PPG will be collected in this patient population with very high HbA1c. This is the first CGM study performed with Soliqua 100/33 in patients with very uncontrolled T2DM (HbA1c \geq 9%-13%) on oral therapies with or without GLP-1 RAs.

3.1.2 Duration of Study Participation for Each Participant

The study comprises the following periods (further detailed in the graphical study diagram [Figure 3–1] and the schedule of events [SoE; Section 13.1]):

- A screening period of up to 2 weeks.
- A run-in period of 2 weeks, including the baseline period.
 - At Visit 2, the CGM device will be applied to the back of the upper arm of the participant and baseline CGM data will be collected continuously for 14 days; the

device will be removed at the subsequent site visit during the baseline period (ie, Visit 3.1), after the MMTT.

- During the baseline period, on Day -1 (Visit 3.1), participants will return to the site for the MMTT (for both β-cell function and PPG measures) and CGM removal and data download (after the MMTT). Dispensing of the Soliqua 100/33 pen and instruction on administration of Soliqua 100/33 will also take place during this visit.
- Visit 3.2 (ie, Day 0) during the baseline period is the first day of Soliqua 100/33 administration and includes a phone contact to ALL participants to ensure all administration procedures were successfully executed and to answer any questions. (Note: The first day of Soliqua 100/33 administration [ie, Visit 3.2, Day 0] for participants on weekly GLP-1 RA will depend on their administration schedule and may not be the day immediately following Visit 3.1. Soliqua 100/33 administration for these participants should be 7 [± 2] days after their last weekly GLP-1RA dose.)
 - A phone contact should also be made ONLY to participants on weekly GLP-1 RA on the day before Soliqua 100/33 initiation, to remind them of the next morning's injection and to provide instructions for SoloStar pen use. The participants will provide their concomitant medication details to the site personnel over the phone.
- A 16-week open-label treatment period.
 - Visit 3.2 (ie, Day 0) is the first day of Soliqua 100/33 administration and begins the open-label treatment period (with different initiation requirements based on weekly or daily GLP-1 RA use, as explained above).
 - The dose of Soliqua 100/33 will be adjusted during the titration period (ie, from Weeks 1 through 12; Visits 4.0 to 5.4), at the investigator's discretion, until the desired fasting SMPG value (80-100 mg/dL) is achieved (Table 5-1).
 - During Visits 4.0 to 4.6, weekly phone contacts for dose adjustments are to continue at the investigator's discretion until the desired fasting SMPG value is achieved.
 - If the desired fasting SMPG value is not achieved in the first 8 weeks of treatment, the investigator has the option to continue weekly dose titration phone contacts for an additional 4 weeks (until Week 12; ie, from Visits 5.1 to 5.4) with the purpose of achieving glycemic targets.

- At Visit 6, a blinded CGM device will again be applied to the back of the upper arm of the participant, and CGM data will be collected continuously for 14 days; the device will be removed at the subsequent site visit (ie, Visit 7), after the MMTT (only to derive PPG measures).
- At the end of the study (ie, Visit 7), participants should discuss with the investigator, in collaboration with their HCP, whether to continue on the Soliqua 100/33 treatment regimen, or transition to an alternate antihyperglycemic therapy.
- A 2-week post-treatment safety follow-up period after the last dose of Soliqua 100/33 (eg, treatment completion) or after premature/permanent treatment discontinuation from Soliqua 100/33.

The total duration of the study will be approximately 22 weeks for each participant.

A detailed description of the assessments performed during each study period and at each visit is provided in Section 13.1.

3.1.3 End of Study Definition

The end of the study is defined as the date of the last visit of the last participant in the study.

4 Selection of Study Population and Discontinuation/Withdrawal

One-hundred participants will be enrolled at approximately 15 sites in the US. Participants will be enrolled in the study only if they meet all of the inclusion criteria and none of the exclusion criteria.

Prospective approval of protocol deviations to recruitment and enrollment criteria, also known as protocol waivers or exemptions, is not permitted.

4.1 Inclusion Criteria

Each participant must meet all of the following criteria to be enrolled in this study:

- 1. Is capable of understanding the written informed consent, provides signed written informed consent, is willing and able to complete the electronic diary (eDiary), and agrees to comply with protocol requirements (confirmed by the site staff performing the recruitment efforts).
- 2. Is an adult ≥ 18 years of age.
- 3. Has an HbA1c \geq 9%-13% during the run-in period.
- 4. Was diagnosed with T2DM at least 6 months before the baseline period.
- 5. Has been treated with 2+ OADs with or without GLP-1 RAs with stable doses (for both) for 3 months before the screening period.
- 6. Is willing and able to wear the CGM device continuously for 14 days to capture CGM measures at baseline (from Visit 2 [ie, the run-in period] until the next site visit at Visit 3.1) and again at the end of the treatment period [ie, from Visit 6 until the next site visit at Visit 7; Section 13.1).
- 7. Is willing and able to prick fingers a minimum of 2 to 4 times per week, using sterile lancets provided with a manual blood glucose meter kit.
- 8. Is willing to discontinue daily (oral or injectable) or weekly GLP-1 RA or DPP-4i before administration of Soliqua 100/33.

9. Is willing and able to inject Soliqua 100/33 and increase dose as needed to achieve SMPG target.

10. If female, is not pregnant or breastfeeding and one of the following conditions applies:

- Is a woman of non-childbearing potential (WONCBP), as defined in contraceptive and barrier guidance (Section 13.7).
- Is a woman of childbearing potential (WOCBP) and agrees to use a contraceptive method that is highly effective, with a failure rate of <1%, as described in contraceptive and barrier guidance (Section 13.7), during the study treatment period (to be effective before starting the study drug) and for at least 1 week after the last administration of study drug.
 - A WOCBP must have a negative urine pregnancy test at both screening and baseline visits. (Note: If a urine test cannot be confirmed as negative [eg, an ambiguous result], a serum pregnancy test is required. In such cases, the participant must be excluded from participation if the serum pregnancy result is positive.)

4.2 Exclusion Criteria

Participants meeting any of the following criteria will be excluded from the study:

- 1. Has T1DM or any other types of diabetes except T2DM.
- 2. Is being treated with meglitinides (eg, nateglinide, repaglinide).
- 3. Has a body mass index (BMI) >40 kg/m² during the screening period.*

*Body weight and height will be recorded during the screening period for the calculation of BMI (metric: BMI = weight (kg)/height [m²]).

 Provides less than equivalent of 8 days of evaluable CGM data (not necessarily consecutive) over a 14-day period (eg, days of CGM device wear × % time CGM device active < 8; Section 6.2.1).

- 5. Has any current or previous skin conditions, including (but not limited to) severe psoriasis, burns, eczema, scarring, and excessive tattoos, that would inhibit proper wearing of the CGM device.
- 6. Has a history of severe nausea and vomiting that resulted in discontinuation of GLP-1 RA.
- 7. Has a known history or presence of clinically significant pancreatitis or gastroparesis.
- 8. Has had an episode of severe hypoglycemia or hypoglycemia unawareness (defined as the onset of neuroglycopenia before the appearance of autonomic warning symptoms [for example, blurred vision, difficulty speaking, feeling faint, difficulty thinking, and confusion] or as the failure to sense a significant fall in blood glucose below normal levels) within the 6 months before the screening period.
- 9. Has any clinically significant abnormality identified from the physical examination, vital sign measurements, or laboratory tests (eg, amylase, lipase, alanine aminotransferase [ALT] >3 × upper limit of normal [ULN], calcitonin ≥20 pg/mL, severe renal impairment [estimated glomerular filtration rate, <30mL/min/1.73m²], or end stage renal disease) or visual impairment at screening that, in the opinion of the investigator or any qualified designee, would make implementation of the protocol or interpretation of the study results difficult or would preclude safe participation in the study.
- 10. Has personal or immediate family history of medullary thyroid cancer (MTC) or a genetic condition that predisposes the participant to MTC (eg, multiple endocrine neoplasia syndromes).
- 11. Has current or known history of alcohol or drug abuse within 6 months before the screening period.
- 12. Has significant current (within past 2 months) or expected use of medications known to affect glycemia (eg, ≥5 mg/day prednisone).
- 13. Uses substances known to interfere with CGM readings, such as aspirin-containing products (>650 mg/day of salicylic acid) or supplements containing vitamin C (>1000 mg/day of ascorbic acid) taken during the 14-day periods of CGM measure at baseline (ie, Visit 2 to Visit 3.1) and the end of the treatment period (ie, Visit 6 to Visit 7).

- 14. Has undergone previous treatment with any insulin (except for short-term treatment due to intercurrent illness, including gestational diabetes, at the discretion of the investigator).
- 15. Is enrolled in another clinical study or has taken other investigational drug(s) within 1 month or 5 half-lives from screening, whichever is longer.
- 16. Is currently in an institution because of a regulatory or legal order (ie, is a prisoner or participant who is legally institutionalized).
- 17. Is an employee or family member of the investigator or study site personnel.
- 18. Is not suitable for participation, whatever the reason, as judged by the investigator, including medical or clinical conditions, or potentially is at risk of noncompliance to study procedures.
- 19. Is involved in a specific situation during study implementation or the course of the study that may raise ethics considerations.
- 20. Has a hypersensitivity to Soliqua 100/33, either of its active components (insulin glargine or lixisenatide), or any of its excipients that, in the opinion of the investigator, contraindicates participation in the study.
- 21. Has used weight loss drugs (including over-the-counter [OTC] and herbal medications) within 12 weeks before the screening visit.

4.3 Screen Failure

Screen failures are defined as participants who consent to participate in the clinical study but are not subsequently enrolled. A minimal set of screen failure information is required to ensure transparent reporting to meet Consolidated Standards of Reporting Trials (CONSORT) publishing requirements and to respond to queries from regulatory authorities. Minimal information includes demography, screen failure reasons, eligibility criteria, and any serious adverse events (SAEs).

Participants who are screen failed may be rescreened based on a discussion between the medical monitor and the investigator.

4.4 Discontinuation From Study Treatment and/or Withdrawal From the Study

4.4.1 Discontinuation From Study Treatment

4.4.1.1 Permanent Discontinuation

All efforts should be made to keep participants on treatment.

In rare instances, it may be necessary for a participant to permanently discontinue study treatment. Before permanent discontinuation of treatment regardless of the reason or as soon as possible after the decision for discontinuation has been made, if possible, the participant will undergo all procedures planned for the last dosing day with Soliqua 100/33 and the follow-up visit (Section 13.1).

All cases of permanent treatment discontinuation (Section 4.4.3) must be recorded by the investigator in the appropriate pages of the electronic case report form (eCRF) when confirmed.

4.4.1.2 Temporary Discontinuation

Temporary study drug discontinuation decided by the investigator corresponds to more than 1 dose not administered to the participant.

Temporary study drug discontinuation may be considered by the investigator because of suspected AEs or for other reasons. In case of study drug interruption due to an AE, reinitiating Soliqua 100/33 treatment at the appropriate dose will be done under close and appropriate clinical/and or laboratory monitoring if the investigator deems the relationship of the event to Soliqua 100/33 as unlikely and if the study inclusion criteria are still met.

The duration of temporary study drug discontinuation should be recorded in the appropriate eDiary pages when confirmed.

4.4.2 Lost to Follow-up

A participant will be considered lost to follow-up if they repeatedly fail to return for scheduled visits and are unable to be contacted by the study site.

The following actions must be taken if a participant fails to return to the clinic for a required study visit:

- The site must attempt to contact the participant and reschedule the missed visit as soon as possible. The participant should be counselled on the importance of maintaining the assigned visit schedule and asked whether they wish to and/or should continue in the study.
- Before a participant is deemed lost to follow-up, the investigator or designee must make every effort to regain contact with the participant. The methods to contact the participants include 2 phone calls and, if necessary, a certified letter to the participant's last known mailing address or local equivalent methods. These contact attempts should be documented in the participant's medical record.

If the participant continues to be unreachable, they will be considered to have withdrawn from the study.

4.4.3 Handling of Withdrawals

Participants are free to withdraw from the study or study treatment at any time upon request. Their participation in the study may be stopped at any time at the discretion of the investigator or at the request of the sponsor.

If the participant withdraws consent for disclosure of future information, the sponsor may retain and continue to use any data collected before such a withdrawal of consent.

If a participant withdraws from the study, they may request destruction of any samples taken and not tested, and the investigator must document this in the site study records.

Participants who discontinue study treatment or active participation in the study will no longer receive study drug. When a participant withdraws from the study, the reason(s) for withdrawal shall be recorded by the investigator on the relevant page of the eCRF.

A participant may withdraw from the study or study treatment under the circumstances (including, but not limited to) listed below:

- The participant intends to become pregnant.
- The participant may be withdrawn at the discretion of the investigator due to noncompliance or due to a safety concern.
- The participant will be withdrawn if starting any drugs that interfere with glucose metabolism (eg, steroid doses equivalent to prednisone ≥5 mg/day).
- The participant may be withdrawn if diagnosed with acute pancreatitis (defined as meeting 2 of the following 3 rules: typical abdominal pain; amylase/lipase >3 × ULN; and/or characteristic ultrasound, computed tomography, or magnetic resonance imaging findings).
- If the fasting or the mean SMPG value during 3 consecutive days is >300 mg/dL, the investigator will schedule an unplanned visit as soon as possible to obtain confirmatory FPG and investigate the cause. If no apparent or intercurrent cause is detected, the participant may be withdrawn.
- The participant has recurrent severe hypoglycemia or recurrent nocturnal hypoglycemia during the treatment period that poses a potential risk to the participant, as judged by the investigator.
- The participant is unable to comply with the study protocol, at the investigator's discretion.

Whenever possible, all participants who discontinue study treatment or withdraw from the study prematurely will undergo all end-of-study and follow-up assessments. Participants who fail to return for final assessments will be contacted by the site in an attempt to have them comply with the protocol.

Participants who withdraw from the study treatment should be explicitly asked about the contribution of possible AEs to their decision, and any AE information elicited must be documented on the relevant page of the eCRF.

It is vital to obtain follow-up data on any participant who is withdrawn because of an AE or SAE. In every case, efforts must be made to undertake protocol-specified, safety, and follow-up procedures.

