
CGM data will require device reinsertion. Eligibility and analysis criteria for CGM measures are provided in Section 13.9.

No. of Days CGM Device Worn ^a	Time CGM Device Active (%) ^a	Equivalent Days
8	100	8.00
9	89	8.01
10	80	8.00
11	73	8.01
12	67	8.04
13	62	8.01
14	57	7.98

Table 6-1Criteria for CGM Device Reinsertion

Abbreviations: AGP, Ambulatory Glucose Profile; CGM, continuous glucose monitoring. ^a AGP report.

Figure 6–1 Criteria for CGM Device Reinsertion

Abbreviation: CGM, continuous glucose monitoring.

Participants with less than equivalent of 8 days of evaluable CGM data (not necessarily consecutive) of a 14-day period (eg, days of CGM device wear \times % time CGM device active < 8) during the run-in period will be considered as screen failures. For participants

Sanofi	SOLIQUA TM 100/33
Protocol: LPS16990 (Original, Version 1.0)	18 Aug 2021

who discontinue study treatment prematurely, the visit window can be extended by 14 days to collect the CGM data before they permanently discontinue the treatment.

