The following intercurrent events for the primary estimand will be handled by the treatment policy strategy: initiation of rescue medication other than the study IMP, discontinuation of IMP, withdrawal from the study, and recording of <80% of evaluable CGM data per 24-hour period over 10 days of a 14-day period, during the run-in period as well as the end of the treatment period (ie, from Weeks 14 to 16; Section 13.9). This estimand aims to reflect the estimated treatment effect under the intention-to-treat (ITT).

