eDiary completion	<					X					>
Daily IMP dosing ^t				<		>	X		>		
IMP dose adjustments					X	Х	Х			Х	
Concomitant medications			х	X	x	х	х	х	Х	х	Х
IMP adherence assessment						х		Х	х		
FPG ^v			Х					-	Х		
DM-SAT ^w			X					-	X		

Sanofi Protocol: LPS16990 (Original, Version 1.0)

Run-in			i-in	Treatment ^a							
Study Period	Screening			Baseline		Titration ^t	•				
Visit ^c	1	2	3.1 ^d	3.2 ^{e,f}	4.0-4.6 ^g	5	5.1-5.4 ^h	6	7 ⁱ	Unscheduled ^j	8
Visit Type	Clinic	Clinic or Home	Clinic	Phone ^e	Phone	Clinic or Home	Phone	Clinic or Home	Clinic	Clinic or Home	Phone
Week	-4	-2	0	0	1 to 7	8	9 to 12	14	16		18
Day	-28	-15 ^k	-1	0	1 to 49	56	63 to 84	98	112		126
Window (Days)				7 ^{(±2)e}		±3		±3	±3		±3
Hypoglycemia events ^x	х	х	х	Х	х	х	х	х	х	х	х
Recording of AEs/SAEs (including AESIs)	x	х	х	х	х	х	х	Х	х	х	х
Product complaints					Х	Х	Х	Х	Х		
Vital signs (including heart rate, systolic and diastolic BP)	х		х						х		
Calcitonin	Х										
Clinical chemistry	Х		Х						Х		
Hematology	Х		Х						Х		
Urinalysis ^y	Х		Х						Х		
Pregnancy test ^z	Х		Х			Х			х		

Abbreviations: ADA, American Diabetes Association; AE, adverse event; AESI, adverse event of special interest; BMI, body mass index; BP, blood pressure; CGM, continuous glucose monitoring; DM-SAT, Diabetes Medications Satisfaction Questionnaire; DPP-4i, dipeptidyl peptidase-4 inhibitor;

DTP, direct-to-patient; eDiary, electronic diary; FPG, fasting plasma glucose; GLP-1 RA, glucagon-like peptide-1 receptor agonist; Hb, hemoglobin;

HbA1c, glycated hemoglobin; HCP, healthcare provider; IMP, investigational medicinal product; MMTT, mixed-meal tolerance test; OAD, oral antidiabetic drug; PPG, postprandial glucose; SAE, serious adverse event; SMPG, self-measured plasma glucose; SU, sulfonylurea.

^a For participants who discontinue study treatment prematurely, the visit window can be extended by 14 days to collect the CGM data, followed by MMTT data, before they permanently discontinue the treatment. Before permanent discontinuation of treatment regardless of the reason or as soon as possible after the decision for discontinuation has been made, if possible, the participant will undergo all procedures planned for the last dosing day with Soliqua 100/33 and the follow-up visit (ie, Visit 7 and above).

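### Participants who stop Soliqua early are assessed at the stop and not clearly kept for Visits 6-7, so a decision to stop before about Day 81-90 yields no usable Week 16 CGM under a treatment-policy estimand

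*Protocol*

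**What the plan says.** **Trigger.** Protocol 4.4.3 lists circumstances for leaving the study or the study treatment. Its lead-in is permissive and several bullets are discretionary, but one is not: "The participant will be withdrawn if starting any drugs that interfere with glucose metabolism". Its example is a steroid dose equivalent to prednisone 5 mg/day or more, with no minimum duration.

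**Timing of final assessments.** Protocol 4.4.1.1 asks for the last-dosing-day and follow-up procedures before a permanent stop or "as soon as possible after the decision for discontinuation has been made". Protocol 6.2.1, repeated in 13.9, adds that "the visit window can be extended by 14 days to collect the CGM data before they permanently discontinue the treatment". Schedule of Events footnote a says the same for both tests: "the visit window can be extended by 14 days to collect the CGM data, followed by MMTT data". Protocol 3.1.2 then gives a 2-week safety follow-up, counted from the last dose or "after premature/permanent treatment discontinuation from Soliqua 100/33".

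**Retention.** The closing paragraph of 4.4.3 says: "Whenever possible, all participants who discontinue study treatment or withdraw from the study prematurely will undergo all end-of-study and follow-up assessments". It gives no date.

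**Estimand.** Protocol 8.1 applies a treatment-policy strategy to events that include "initiation of rescue medication other than the study IMP, discontinuation of IMP, withdrawal from the study". The SAP Table 3 footnote keeps rescue and drug discontinuation but omits study withdrawal. SAP 4.3.1 says that assessments made after stopping drug will be used.

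**Week 16 data and imputation.** SAP 4.3.1 takes Week 16 CGM from Day 95 onward and requires 8 full days, 9 days at 89% or more, or 10 days at 80% or more. Protocol 8.7.2.1 and 8.7.3.3 name treatment discontinuation as a reason for carrying the baseline value forward. SAP 4.3.2 does so for all missing data not due to technical problems, which makes the change 0.

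**The concern.** A treatment-policy estimand for drug discontinuation needs the outcome at Week 16 from people who are no longer on drug. The SAP is ready to analyse such data, but the protocol's procedures collect the last CGM around the stop and then lead to a short safety follow-up. For most of the treatment period, that CGM falls before the SAP's Week 16 window opens.

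An outcome that could have been observed at visits already in the schedule is then replaced by an assumed value or dropped. The three CGM-based key secondary endpoints follow the same missing-data approach (SAP 4.4.1.2). For the meal test, the SAP accepts early-termination data from Day 56; it has no matching rule for CGM. An HbA1c drawn at an early stop can also miss the Week 16 window of Days 103-116 (SAP Table 8), though HbA1c is only a tertiary/exploratory endpoint.

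**Working it through.** **1. The plan's sample size.** Inputs from Protocol 8.3: difference 10 points, SD 25, two-sided 0.05, 95% power, 15% loss.
- Normal approximation: n = (25 × (1.960 + 1.645) / 10)² = 81.2, so 82, as stated.
- The exact t-test power at n=82 is 94.7%, close to the stated 95%.
- 82 / 0.85 = 96.5, so 97; the plan enrols 100.

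**2. Which stops can yield Week 16 CGM.** Let D be the day of the decision to stop, with CGM running to D+14 under the full extension. Days available from Day 95 onward = D + 14 − 95 + 1. For k days, D must be at least 95 + k − 1 − 14.

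| Needed from Day 95 | k | Earliest D | Share of the 112 treatment days |
|---|---|---|---|
| any reading | 1 | 81 | 81/112 = 72% |
| 8 full days | 8 | 88 | 88/112 = 79% |
| 9 days at 89% or more | 9 | 89 | 89/112 = 79% |
| 10 days at 80% or more | 10 | 90 | 90/112 = 80% |

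The last column is a share of time, not of participants. These are decision days: Protocol 6.2.1 collects the CGM before the drug is permanently stopped, so the last dose could come up to 14 days later. The cut-offs move by about a day if wear ends at D+13, or because the protocol counts first dose as Day 0 and the SAP as Day 1. If the SAP's Day 95 refers to the start of the sensor session, the cut-off is Day 95 itself, so the table is generous to the plan.

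Example: for a decision on Day 21, planned contact ends at 21 + 14 = Day 35, or 21 + 14 + 14 = Day 49 with the extension. Visit 6 is on Day 98, which is 49 to 63 days later.

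**3. Effect of setting a share p to change 0.** The documents give no rate for the glucose-interfering-drug trigger, so 1-5% is an assumption. The upper case is the 15% that Protocol 8.3 expects to discontinue for any reason. Carried-forward participants stay in the analysis, so n=100 is used, assuming that all 100 enter the efficacy set and none is lost for technical reasons.

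Mean = 10(1 − p); variance = 625(1 − p) + 100p(1 − p); one-sample two-sided t-test at 0.05.

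| p | Mean | SD | Power, n=100 |
|---|---|---|---|
| 0 | 10.0 | 25.0 | 97.7% |
| 1% | 9.9 | 24.9 | 97.6% |
| 3% | 9.7 | 24.7 | 97.3% |
| 5% | 9.5 | 24.5 | 97.0% |
| 15% | 8.5 | 23.3 | 95.0% |

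One participant set to 0 whose true change would have been 10 points moves the mean by 10/100 = 0.10 points. If the true change would have been 0, there is no bias.

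**4. If these participants are excluded instead.** With all 15% excluded, 100 × 0.85 = 85 remain, still above the planned 82. The question is then how those excluded differ from those kept.

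**The case against.** Several parts of the case for the plan stand.

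- **Change 0 is not certain.** A reader might infer that these participants are definitely analysed as zeros. SAP Table 3 computes the mean for participants with compliant CGM at both baseline and Week 16, and SAP 4.3.2 defines technical missingness as failing the compliance rule. Either text could exclude them. Carrying baseline forward is the natural reading, because the protocol names treatment discontinuation as a reason for it. On both readings no observed Week 16 outcome is used.
- **The protocol does not bar Week 16 assessments.** The lead-in to 4.4.3 covers the study or the study treatment, so the mandatory bullet may mean stopping drug only. Section 4.4.3 also asks for end-of-study assessments where possible and, for withdrawals due to adverse events, for efforts in every case. But neither request sets a date, and the one provision that does, 4.4.1.1, points to the stop.
- **The steroid bullet may rarely apply.** Exclusion 12 already screens out "expected use of medications known to affect glycemia", and Protocol 5.11 lets the investigator give any medication needed for the participant's welfare. A reader might treat this bullet as the main problem; it is one trigger among several, with no documented rate.
- **Power is not the issue.** A reader might add the zeros to the planned n=82. That would double-count, because the 82 are evaluable completers after the 15% loss, whereas carried-forward participants remain in the analysed set.
- **A sensitivity analysis exists.** Protocol 8.7.2.2 would use evaluable CGM from early discontinuers, but only if missing CGM data are substantial. The matching analysis in SAP 4.3.3 excludes missing Week 16 data and does not mention early CGM. Neither recovers readings that were never taken.
- **The SAP's event list is narrower.** It omits study withdrawal, so outcomes after that could be viewed simply as missing data with a prespecified rule. That does not answer the case of drug discontinuation, which both documents keep under treatment policy.

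**Conclusion.** The point holds as a minor mismatch between the estimand and the data collection. As written, a decision to stop before about Day 81 leaves no Week 16 CGM, and one before about Day 88-90 leaves too little to be compliant, even with the full 14-day extension. No text clearly asks the participant to return for Visits 6-7.

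The numerical effect is small. At n=100 and a true 10-point change, the mean falls to 9.9-9.5 for an assumed 1-5% affected and to 8.5 for the whole planned 15%. Power stays at 95.0% or above. The bias works against the drug only if the unobserved changes are positive and baseline is carried forward; under exclusion, the direction is unknown.

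This rests on the Day 95 rule applying to CGM days, on 4.4.1.1 governing the date of the final assessments, and on an assumed rate. It does not show that the primary test is at risk.

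**What to change.** - **Protocol 4.4.3:** state that starting a glucose-interfering drug may lead to stopping study drug but does not by itself end study participation.
- **Protocol 4.4.1.1, 6.2.1, 13.9 and Schedule of Events footnote a** (with the matching synopsis text and the schedule copied in the SAP): state that all consenting participants who stop study drug keep the scheduled Visit 6-7 CGM and the Visit 7 HbA1c, in addition to the procedures at the stop.
- **Protocol 3.1.2:** state that the 2-week follow-up after an early stop is a safety contact, not the end of participation.
- **Meal test:** do not require it at Visit 7 off drug. Protocol 6.2.2 has Soliqua given 30 minutes before the meal, and 4.4.3 says those who stop receive no more. Keep the early-termination test with the SAP's Day 56 rule.

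SAP 4.3.1 already accepts CGM collected after drug discontinuation, so its endpoint definition need not change.

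**Cost:** one protocol amendment with IRB review and a reminder to sites, with no visits beyond those already scheduled. Some Week 16 CGM will be off-drug or steroid-affected, which is what a treatment-policy estimand intends.
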